### 5.9.12 Laboratory Evaluations

Blood samples for haematology and clinical chemistry and urinalysis will be taken at scheduled visits and analysed at the local laboratory using standard methods for routine tests. **NB. Laboratory tests for screening or entry into the trial should be performed within 10 days prior to the first dose of treatment, on dosing days for all cycles, samples must be taken pre-dose (up to 72 hours prior to dosing).** Samples must be processed, and results available, prior to study treatment administration to ensure and confirm an assessment of patient suitability. In circumstances where blood samples for haematology and clinical chemistry and urinalysis fulfils both the timeline of day -10 to 0 and 72 hours prior to C1D1 dosing these can be used to cover both screening and C1D1.

The following variables will be measured at the time-points indicated in Table 3.

- Biochemistry: Sodium [Na], potassium [K], chloride [Cl], bicarbonate [CO2]‡, Uric Acid, calcium, phosphate, glucose), Alanine aminotransferase (ALT), Aspartate aminotransferase (AST), alkaline phosphatase, albumin, Lactate dehydrogenase (LDH), total bilirubin, direct bilirubin (*If total bilirubin is elevated above the upper limit of normal*), total protein, magnesium
- Haematology: White blood cell count (WBC) with differential (to include neutrophils, lymphocytes, monocytes, eosinophils, basophils), red blood cell (RBC) count haemoglobin (Hgb), haematocrit (Hct), Absolute neutrophil count (ANC), Absolute lymphocyte count (ALC) and platelet count.
- Coagulation: PT/INR and aPTT
- Urinalysis: Macroscopic assessment of the amount of protein, glucose, white blood cells and blood if they are present (levels should be recorded if available) and microscopic analysis should be performed if an abnormality is noted.
- Pregnancy test for patients of child-bearing potential (***If urine pregnancy results cannot be confirmed as negative, a serum pregnancy test will be required.*** Serum  $\beta$ -human chorionic gonadotropin ( $\beta$ -hCG) for patients of child-bearing potential
- Thyroid: Total triiodothyronine (T3), Free thyroxine (FT4), Thyroid stimulating hormone (TSH)
- Tumour Markers for CUP +/- any serum markers deemed to be relevant to disease monitoring, e.g. PSA, b-HCG, CEA, Ca19.9, Ca125, Ca153, AFP, NSE, SCC, S100, and Chromogranin A and B.
- ‡ *If considered standard of care in your region.*

CUPem	C/37/2017	Imperial College London	V7.0, 08.12.2021
-------	-----------	----------------------------	------------------

Laboratory values that have changed significantly from baseline and are considered to be of clinical concern must be recorded as an adverse event and followed up as appropriate.

#### **5.9.13 Treatment Compliance (Patient Diary)**

Patients will be required to keep a detailed record of all study treatment that they take in a patient diary. Date and time of administration and drug dose will be collected.

#### **5.9.14 Quality of Life**

The QOL instrument, EORTC QLQ-C30 version 3 will be administered as specified in Table 3 and must be completed before other assessments are performed or study drug is administered.

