##### **Cohort 2:**

Cohort 2 is now formally closed. This cohort had sought to enrol patients who are chemo-naïve (first-line setting) for CUP, with a PS 0-2.

\*\*\*\*\*

Patients will undergo screening procedures during a standard 28-days time window from initiation of the study, under standard GCP and informed consent. Restaging will be performed by computerized tomography using ir-RECIST criteria at 3 months from initiation of systemic treatment and on an 8 weekly basis thereafter until radiological proven disease progression or intolerance or patient choice.

The EORTC QLQ-C30 questionnaire (to assess the quality of life) will be done at baseline after 3 months and then at discontinuation of study treatment.

Correlative translational study samples (blood) and tissue (used for histological confirmation and to document PD-L1 expression) will be collected at baseline, and blood and serum samples monthly (after an informed optional consent and banked for retrospective immune-modulating and other biomarkers for future research and analysis). Patients will also be separately consented to the NHSE CUP 100K genome project that will be running in the UK by 2018, for deep sequencing of tumor tissue and germ-line, in centers participating in, or with access to the UK framework for this programme.

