### **5.3 Treatment Period**

Patients will receive their study treatment until disease progression, unacceptable toxicity or withdrawal. Patients will be required to attend clinic for assessments to be performed during treatment as per Table of Assessments (Table 3).

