## 5.8 Study Schedules during Treatment

Table 3 summarizes the trial procedures to be performed at each visit. Individual trial procedures are described in detail below. Treatment is divided into cycles of 21 days, with visits and assessments specified according to the relevant cycle.

Unless otherwise indicated, scheduled assessments may take place within  $\pm 3$  days of the specified visit. Assessment days are relative to the start of study treatment i.e. Cycle 1 Day 1.

If a patient has a treatment break, please contact the Clinical Trials Section (CTS) for advice regarding the timing of research blood assessments. All other assessments, including laboratory safety assessments, vital signs and radiological imaging should continue to be performed.

CUPem	C/37/2017	Imperial College London	V7.0; 08.12.2021
-------	-----------	----------------------------	------------------

Furthermore, additional evaluations/testing may be deemed necessary by the Sponsor and/or MSD for reasons related to subject safety. In some cases, such evaluation/testing may be potentially sensitive in nature (e.g., HIV, Hepatitis C, etc.), and thus local regulations may require that additional informed consent be obtained from the subject. In these cases, such evaluations/testing will be performed in accordance with those regulations.

**During the COVID-19 pandemic, patients whom are under ongoing treatment can be offered longer intervals of 1 to 2 weeks between treatment to avoid peak COVID-19 capacity issues.**

CUPem	C/37/2017	Imperial College London	V7.0; 08.12.2021
-------	-----------	----------------------------	------------------

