**Table 3: Table of Assessments**

Trial Period:	Screening Phase	Treatment Cycles								End of Treatment	Post-Treatment		
Treatment Cycle/Title:	Study Screening	1	2	3	4	To be repeated beyond 8 cycles				Discon	Safety Follow-up	Follow Up Visits	Survival Follow-Up
						5	6	7	8				
Scheduling Window (Days):	-28 to -1		± 3	± 3	± 3	± 3	± 3	± 3	± 3	At time of Discon	30 days post discon	Every 8 weeks post discon	Every 12 weeks
Administrative Procedures													
Pre-screening Visit													
Informed Consent	X												
Inclusion/Exclusion Criteria	X												
Demographics and Medical History	X												
Prior and Concomitant Medication Review	X	X	X	X	X	X	X	X	X	X	X		
Trial Treatment Administration		X	X	X	X	X	X	X	X				
Trial Treatment Compliance		X	X	X	X	X	X	X	X				
Quality of Life Questionnaire (EORTC QLQ-C30)	X					X				X			
Post-study anticancer therapy status											X	X	X
Survival Status		X	X	X	X	X	X	X	X	X	X	X	X
Clinical Procedures/Assessments													
Review Adverse Events	X	X	X	X	X	X	X	X	X	X	X		
Full Physical Examination	X a	X			X				X	X	X		
Directed Physical Examination	X a	X	X	X	X	X	X	X	X	X	X	X	
Vital Signs and Weight	X a	X	X	X	X	X	X	X	X	X	X	X	
ECOG Performance Status	X a	X	X	X	X	X	X	X	X	X	X	X	
Laboratory Procedures/Assessments: analysis performed by LOCAL laboratory													
Pregnancy Test –Serum β-HCG	X b		X c		X c		X c		X c				
PT/INR and aPTT	X d	X e	X e	X e	X e	X e	X e	X e	X e	X	X	X	
CBC with Differential	X d	X e	X e	X e	X e	X e	X e	X e	X e	X	X	X	

CUPem	C/37/2017	Imperial College London	V7.0, 08.12.2021
-------	-----------	----------------------------	------------------

Trial Period:	Screening Phase	Treatment Cycles								End of Treatment	Post-Treatment		
Treatment Cycle/Title:	Study Screening	1	2	3	4	To be repeated beyond 8 cycles				Discon	Safety Follow-up	Follow Up Visits	Survival Follow-Up
						5	6	7	8				
Scheduling Window (Days):	-28 to -1		± 3	± 3	± 3	± 3	± 3	± 3	± 3	At time of Discon	30 days post discon	Every 8 weeks post discon	Every 12 weeks

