#### **5.9.15 Tumour Assessments**

Tumour assessments will be performed using CT contrast or MRI scans of the chest, abdomen and pelvis at the time-points indicated in Table 3. The same method used for assessment at baseline must be used at all subsequent time points.

Tumour assessment will include: if disease is measurable or non-measurable (at least one lesion must be measurable), date of assessment, imaging method used, site (breast, lung, liver, pleural effusion, local lymph nodes, distant lymph nodes, bone, brain or other site), longest diameter of each target lesion and sum of longest diameters for all target lesions.

Patient response to treatment will be assessed using RECIST v1.1. Tumour size, progression free survival and objective response rate will all be determined. The RECIST v1.1 (January 2009) guidelines for measurable, non-measurable, target and non-target lesions and the objective tumour response criteria (complete response, partial response, stable disease or progression of disease) are detailed in Appendix A.

Tumour size will be assessed at baseline and on scans at subsequent time points and recorded as the sum of the longest diameters of the target lesions. Baseline assessment should be performed no more than 28 days before the start of study treatment and ideally as close as possible to the start of study treatment; it should include all areas known for possible breast cancer metastases. Subsequent tumour assessments will be conducted every 12 weeks from C1D1, the window for each assessment is  $\pm 7$  days. During the period of the COVID-19 pandemic, this window period can be increased from -1 to a 2 week interval.

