5.1 Primary Efficacy Endpoint

The overall response to treatment is assessed using RECIST v1.1 and immune-related (irRECIST). Appendices A and B in the protocol present the guidelines for evaluation of objective tumour response Using RECIST 1.1 (Response Evaluation Criteria in Solid Tumours) or immune-related RECIST. The disease control rate will be calculated.

Disease Control Rate (DCR) - is defined as the proportion of patients in whom the best overall response is determined as complete response (CR), partial response (PR) or stable disease (SD) for at least 12 weeks in either RECIST or irRECIST criteria.

Overall Survival (OS) - defined as the length of time from study enrolment until death, withdrawal of consent, last follow-up date if lost to follow-up or the end of the study, whichever occurs first.

Progression Free Survival (PFS) – is defined as the length of time from study enrolment to first evidence of progressive disease identified at follow-up or confirmed disease progression at the end of the trial or death. Patients will be censored at the last follow-up date if they are lost to follow-up, withdrawn from the study or have not progressed at the end of study. Median PFS and its 95% confidence interval will be reported. Kaplan-Meier survival curves will also be plotted.

Quality of Life (QOL) is measured as scores from the EORTC QLQ-C30 version 3 questionnaire which will be administered at baseline, after 3 months and then at discontinuation of study treatment.

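### The month-3 quality-of-life form is tied to the cycle 5 visit, so patients off treatment by week 12 have no month-3 value and the comparison is conditional on staying on treatment

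*Protocol*

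**What the plan says.** Rapid improvement in quality of life is part of the primary hypothesis (Protocol 2.1, SAP 2.1). The SAP lists quality of life under the primary efficacy endpoint (5.1) and the primary efficacy analysis (6.3).

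The narrative text gives calendar times. Protocol 3.1 says the form "will be done at baseline after 3 months and then at discontinuation of study treatment", and SAP 5.1 says it is "administered at baseline, after 3 months and then at discontinuation of study treatment". Protocol 5.9.14 sends sites to Table 3 instead: the form "will be administered as specified in Table 3 and must be completed before other assessments are performed or study drug is administered". There the row "Quality of Life Questionnaire (EORTC QLQ-C30" has a mark at screening, cycle 5 and discontinuation, and none at the safety follow-up, follow-up or survival visits. A header over cycles 5 to 8 asks for repetition beyond cycle 8, but SAP Table 5 has only Baseline, Month 3 and Discon columns.

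Protocol 5.8 states: "Treatment is divided into cycles of 21 days". Visits have a window of ±3 days. On scans, Protocol 5.9.15 states: "Subsequent tumour assessments will be conducted every 12 weeks from C1D1, the window for each assessment is" ±7 days. The first on-treatment scan is marked in the same cycle 5 column as the form.

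Protocol 5.3 states: "Patients will receive their study treatment until disease progression, unacceptable toxicity or withdrawal". Appendix B lets clinically stable patients continue until progression is confirmed on a repeat scan at least 4 weeks later. Protocol 6.9.6 allows an exception even after confirmation.

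SAP 6.3 compares scores between visits by repeated-measures ANOVA or Friedman's test, in per-protocol patients with a baseline form and at least one later form. SAP 6.8 rules out imputation.

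**The concern.** A form tied to a dosing visit is completed only by patients still being dosed. Those who stop by week 12, most often for progression or deterioration, have no scheduled month-3 form. If they stop close to week 12 they do complete a form at about the right time, but the SAP files it under Discon and has no rule that lets it count as Month 3. The usual forms of both named tests use complete rows, so a patient with only Baseline and Discon drops out of a three-visit test. Changing the test cannot recover a month-3 value that was never collected or never mapped.

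Continuation beyond first progression does not remove the selection. Appendix B makes it depend on symptoms, laboratory values and no decline in ECOG status, so the progressing patients who reach cycle 5 are those judged clinically stable. That is selection on something close to the outcome.

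A second weakness is that the order of form and scan is not fixed. Some patients may answer after learning their result in an open-label trial.

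At stake is whether an apparent month-3 improvement in a primary-hypothesis outcome can be told apart from the departure of patients who were doing badly.

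**Working it through.** **Timing.** SAP 6.1 equates the 12-week scan interval with 4 cycles. Check: 4 × 21 = 84 days = 12 weeks, so the plan's figure reproduces. Cycle 5 day 1 and the first scan share nominal day 84.

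**Order of form and scan.** The visit may fall on days 81 to 87 (7 days) and the scan on days 77 to 91 (15 days), which gives 7 × 15 = 105 day pairs. The two coincide in 7. By symmetry the scan comes first in (105 - 7)/2 = 49 (47%) and the form first in 49 (47%). This counts permitted orderings and does not forecast practice. The rule that the form is completed before other assessments governs a single visit. It does not cover a scan done and disclosed on an earlier day.

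**Dosing delays.** Protocol 5.8 permits treatment intervals longer by 1 to 2 weeks during the pandemic, while scans stay anchored to C1D1. One delayed interval moves cycle 5 to day 84 + 7 = 91 up to 84 + 14 = 98. Four delayed intervals move it to day 84 + 28 = 112 up to 84 + 56 = 140. This pushes towards scan first. Protocol 5.9.15 also relaxes the scan window in the pandemic, which is not used here.

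**Share at risk.** Inputs are the medians in Protocol 8.2, exponential survival (assumption), time counted from C1D1, and t = 84/30.4375 = 2.76 months. The formula is S(t) = 0.5^(t/median).

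| | Null (PFS 2, OS 4 months) | Alternative (PFS 4, OS 7 months) |
|---|---|---|
| Progression-free | 0.5^(2.76/2) = 0.384 | 0.5^(2.76/4) = 0.620 |
| Alive | 0.5^(2.76/4) = 0.620 | 0.5^(2.76/7) = 0.761 |
| Alive with progression | 0.620 - 0.384 = 0.236 | 0.761 - 0.620 = 0.141 |
| Patients of 31 / of 67 | about 7 / 16 | about 4 / 9 |

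**Effect on the month-3 mean.** The changes in score are assumptions, since the documents give none. Mean in all living patients = (progression-free share × its change + progressed share × its change) / alive share.

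- Changes +8 and -12, null: (0.384 × 8 - 0.236 × 12)/0.620 = +0.4. Alternative: (0.620 × 8 - 0.141 × 12)/0.761 = +4.3. If no progressed patient has a month-3 form, the column shows +8.
- Changes +5 and -5, null: 5 × (0.384 - 0.236)/0.620 = +1.2. Alternative: 5 × (0.620 - 0.141)/0.761 = +3.1. The column shows +5.
- Changes +8 and -12, with half of the progressed patients keeping a form, null: (0.384 × 8 - 0.118 × 12)/(0.384 + 0.118) = +3.3. Alternative: (0.620 × 8 - 0.0705 × 12)/(0.620 + 0.0705) = +6.0.

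**The case against.** A reader might infer that the form always follows a scan that has already decided who continues, that every patient progressing on that scan lacks a month-3 value, and that the rest answer after good news. The documents do not support this:

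- Form and scan share a nominal day and the windows allow either order. The requirement that the form "must be completed before other assessments are performed or study drug is administered" can be met whenever the scan is on the same day or later.
- Appendix B and Protocol 6.9.6 let some progressing patients stay on treatment, attend cycle 5 and complete the form.
- No section says when scan results are disclosed.

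Further points on the other side are fair. Patients who stop do complete a discontinuation form, and SAP Table 5 shows it beside Month 3. Three months and cycle 5 agree as nominal dates. Quality of life drives no sample size or go/no-go rule, and the Protocol summary calls the trial hypothesis generating. The 24% and 14% count everyone alive with progression, including any who would still attend cycle 5.

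These points limit the size of the problem but do not remove it. Patients off treatment by week 12 have no scheduled month-3 form, there is no rule for a discontinuation form near week 12, and the order of form and scan result is left open.

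**Conclusion.** The point holds as a design weakness that should be corrected. Followed as written, the plan makes the month-3 comparison conditional on remaining on treatment, so it can show improvement where living patients have on average little or none. Knowledge of the scan result is a possible further bias, not an established one.

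On the assumed +8/-12 changes, the overstatement is at most 8 - 0.4 = 7.6 points (null) or 8 - 4.3 = 3.7 (alternative). It falls to 3.3 - 0.4 = 2.9 or 6.0 - 4.3 = 1.7 if half of the progressed patients keep a form. With +5/-5 the maximum is 5 - 1.2 = 3.8 or 5 - 3.1 = 1.9.

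These figures rest on exponential survival, the plan's medians and score changes that the documents do not supply. They cover loss through progression only and leave out patients who stop for other reasons. The selection itself follows from the schedule and needs none of these assumptions.

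**What to change.** 1. **SAP 5.1, 6.3 and Table 5.** Make baseline to Month 3 the main quality-of-life comparison. Define the Month 3 value as the form completed in the week-12 window (days 77 to 91, or the cycle 5 form if dosing was delayed), whether or not treatment has stopped, including a discontinuation form in that window. Report Discon descriptively or as a separate comparison, so that one form is never entered at two time points in the same test.
2. **Protocol Table 3.** Schedule the form at week 12 (±7 days) from C1D1 regardless of treatment status. For patients who have stopped, collect it at an existing visit, by post or by telephone. Flag forms completed after new anti-cancer therapy, which can itself affect the scores.
3. **Protocol 5.9.14.** State that the form is completed before the scan result is given to the patient.

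Part 1 uses dated forms already collected and can be fixed before analysis. Parts 2 and 3 add at most one questionnaire for patients who stopped early. Some of them will need a remote route, because after confirmed progression or new therapy the only planned contact is the 12-weekly survival call (Protocol 5.5.1).

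Separately, Protocol 3.4 and 5.3 (treatment until progression) and Protocol 6.9.6 and Appendix B (continuation pending confirmation, or by exception) must be reconciled, since they determine who attends cycle 5.

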#### **5.9.15 Tumour Assessments**

Tumour assessments will be performed using CT contrast or MRI scans of the chest, abdomen and pelvis at the time-points indicated in Table 3. The same method used for assessment at baseline must be used at all subsequent time points.

Tumour assessment will include: if disease is measurable or non-measurable (at least one lesion must be measurable), date of assessment, imaging method used, site (breast, lung, liver, pleural effusion, local lymph nodes, distant lymph nodes, bone, brain or other site), longest diameter of each target lesion and sum of longest diameters for all target lesions.

Patient response to treatment will be assessed using RECIST v1.1. Tumour size, progression free survival and objective response rate will all be determined. The RECIST v1.1 (January 2009) guidelines for measurable, non-measurable, target and non-target lesions and the objective tumour response criteria (complete response, partial response, stable disease or progression of disease) are detailed in Appendix A.

Tumour size will be assessed at baseline and on scans at subsequent time points and recorded as the sum of the longest diameters of the target lesions. Baseline assessment should be performed no more than 28 days before the start of study treatment and ideally as close as possible to the start of study treatment; it should include all areas known for possible breast cancer metastases. Subsequent tumour assessments will be conducted every 12 weeks from C1D1, the window for each assessment is  $\pm 7$  days. During the period of the COVID-19 pandemic, this window period can be increased from -1 to a 2 week interval.

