## 13 **APPENDICES**

### **Appendix A: Guidelines for Evaluation of Objective Tumour Response Using RECIST 1.1 (Response Evaluation Criteria in Solid Tumours)**

**Guidance Document Version 2.0 date 17th November 2014**

Response and progression will be evaluated in this study using the new international criteria proposed by the revised Response Evaluation Criteria in Solid Tumours (RECIST) guideline (version 1.1) [Eur J Ca 45:228-247, 2009]. Changes in the largest diameter (unidimensional measurement) of the tumour lesions and the shortest diameter in the case of malignant lymph nodes are used in the RECIST criteria.

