and recorded and measured at baseline. Target lesions should be selected on the basis of their size (lesions with the longest diameter) and be representative of all involved organs, as well as their suitability for reproducible repeated measurements. All measurements should be recorded in metric notation using calipers if clinically assessed.

A sum of the diameters (longest for non-nodal lesions, short axis for nodal lesions) for all target lesions will be calculated and reported as the baseline sum diameters, which will be used as reference to further characterize any objective tumour regression in the measurable dimension of the disease. If lymph nodes are to be included in the sum, only the short axis will contribute.

Non-target lesions All lesions (or sites of disease) not identified as target lesions, including pathological lymph nodes and all non-measurable lesions, should be identified as non-target lesions and be recorded at baseline. Measurements of these lesions are not required and they should be followed as 'present', 'absent' or in rare cases, 'unequivocal progression'.

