### **Response Criteria**

#### **Evaluation of Target Lesions**

Complete Response (CR): Disappearance of all target lesions. Any pathological lymph nodes (whether target or non-target) must have reduction in short axis to <10 mm.

Partial Response (PR): At least a 30% decrease in the sum of the diameters of target lesions, taking as reference the baseline sum diameters

Progressive Disease (PD): At least a 20% increase in the sum of the diameters of target lesions, taking as reference the smallest sum on study (this may include the baseline sum). The sum must also demonstrate an absolute increase of at least 5mm.

Stable Disease (SD): Neither sufficient shrinkage to qualify for PR nor sufficient increase to qualify for PD.

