6.11 Tables to present

Table 1. Patient Baseline Characteristics *

	Cohort 1 n = 20	Cohort 2 n = 57
Age (yr)		
Sex		
Male		
Female		
Weight (kg)		
Height (m)		
BMI (kg/m²)		
Ethnicity		
White		
Mixed		
Asian		
Black		
Other		
Cell Type of Tumour		
Adenocarcinoma		
Squamous cell carcinoma		
Neuroendocrine		
Poorly differentiated carcinoma		
Poorly differentiated neoplasm		
Histopathological types of CUP		
Well or moderately differentiated adenocarcinomas		
Undifferentiated or poorly differentiated adenocarcinomas or carcinomas		
Squamous cell carcinomas		
Undifferentiated neoplasms		
CUP Subtypes		
Poorly differentiated carcinoma, predominantly nodal disease		
Poorly differentiated neuroendocrine carcinomas		
Peritoneal adenocarcinomatosis of a serous papillary histological type in females		
Isolated axillary nodal metastases in females		
Squamous carcinoma involving non- supraclavicular cervical lymph nodes		
Metastases in bone adenocarcinoma and elevated serum PSA in males		
Poor-risk visceral CUP		

* Data are presented as frequency (percentage) for categorical variables and median [IQR] for continuous variables

Table 2. Concomitant medical conditions at baseline*

Medical condition	Cohort 1 n =	Cohort 2 n =
Medical condition 1		
Medical condition 2		
Medical condition 3		
Medical condition 4		
Medical condition 5		
Medical condition 6		
Medical condition 7		
Medical condition 8		

** Data are presented as number of patients having the medical condition.
A patient may have more than one concomitant medical condition.*

Table 3. Concomitant medications at baseline*

Drug Name and Dose	Cohort 1 n =	Cohort 2 n =
Medication 1		
Medication 2		
Medication 3		
Medication 4		
Medication 5		
Medication 6		
Medication 7		

** Data are presented as number of patients taking the medication. A patient may have more than one concomitant medication.*

Table 4. Summary of Tumour Assessment based on RECIST (irRECIST)

	Baseline	Cycle 5	Cycle 8	Discon	Post Discon
Sum of the diameters for all target lesions (mm)[†]	## (##-##) [n=##]	## (##-##) [n=##]	## (##-##) [n=##]	## (##-##) [n=##]	## (##-##) [n=##]
Proportion of Tumour size change^{†‡}		## (##-##) [n=##]	## (##-##) [n=##]	## (##-##) [n=##]	## (##-##) [n=##]
Overall response (n=)					
Complete response		0 (0%)	0 (0%)	0 (0%)	0 (0%)
Partial response					
Stable disease					
Progressive disease					
Progression before scan					
Withdrawn before scan					
Missing					

[†] Data are presented as median (IQR)

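### Protocol 5.9.15 records the longest diameter of every target lesion while Appendix A uses the short axis for nodes, so patients with nodal targets can be misclassified where 5.9.15 is followed literally

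*Protocol*

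**What the plan says.** Protocol 5.9.15 (Tumour Assessments) states the measurement rule twice. Its list of what an assessment includes ends with "longest diameter of each target lesion and sum of longest diameters for all target lesions". Its paragraph on tumour size over time says that size, at baseline and at later scans, is "recorded as the sum of the longest diameters of the target lesions". The sites it lists include "local lymph nodes, distant lymph nodes, bone, brain or other site". Neither sentence makes an exception for nodes.

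The same section also says "Patient response to treatment will be assessed using RECIST v1.1" and points to Appendix A for lesion definitions and response criteria.

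Appendix A takes a different line on nodes. Its introduction says that "the shortest diameter in the case of malignant lymph nodes are used in the RECIST criteria". Under Definition of Disease Parameters it says: "If lymph nodes are to be included in the sum, only the short axis will contribute". A node needs a short axis of at least 15 mm to be a target. For complete response, under Evaluation of Target Lesions: "Any pathological lymph nodes (whether target or non-target) must have reduction in short axis to <10 mm".

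The SAP (5.1) sends response evaluation to Appendices A and B. Its Table 4 reports a sum of diameters without naming the axis used for nodes.

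**The concern.** For a nodal target the two rules cannot both be followed. Section 5.9.15 specifies what a site records, and Appendix A specifies how the category is derived from the record. If only the quantities named in 5.9.15 are on file, the Appendix A sum cannot be formed for a patient with nodal targets, and the nodal condition for complete response cannot be verified.

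The target-lesion sum feeds response rate, DCR and PFS, all of which sit under the primary objectives. It also feeds SAP Table 4, the tumour-size distribution (Figure 3) and the waterfall plot (Figure 4). Appendix B compares the same sum with its smallest value when confirming progression, so irRECIST inherits the problem.

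Nodal disease is expected in this population: SAP Table 1 has a row for "Poorly differentiated carcinoma, predominantly nodal disease" and two further subtype rows defined by nodal sites. Sites reading different sections could report different categories for the same scan. The documents commit to no central review that would catch this. Appendix A only recommends independent review where objective response is the primary endpoint.

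**Working it through.** The plan states no figure on this point, so there is nothing to reproduce. The check applies Appendix A's thresholds to the same lesions under each rule.

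**Inputs from Appendix A (Evaluation of Target Lesions)**
- PR: sum down by at least 30% from baseline.
- PD: sum up by at least 20% from the smallest sum on study, and by at least 5 mm.
- Target-lesion CR: all targets gone, with nodal short axes below 10 mm.

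**Assumptions.** All lesion sizes are mine (long x short axis, mm), and baseline is taken as the smallest sum. Every node has a baseline short axis of at least 15 mm, so each qualifies as a target.

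**Formulas**
- Section 5.9.15: L = sum of longest diameters over all targets.
- Appendix A: A = longest diameters of non-nodal targets + short axes of nodal targets.
- Change = (later sum - baseline sum) / baseline sum.

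With no nodal target, L = A and the conflict has no effect.

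| Case | L (5.9.15) | A (Appendix A) |
|---|---|---|
| 1. One node, 30x20 to 26x13 | 30 to 26: -4/30 = -13.3%, SD | 20 to 13: -7/20 = -35.0%, PR |
| 2. One node, 30x20 to 37x21 | 30 to 37: +7/30 = +23.3%, +7 mm, PD | 20 to 21: +1/20 = +5.0%, +1 mm, SD |
| 3. Two nodes, each 30x20 to 32x25 | 60 to 64: +4/60 = +6.7%, SD | 40 to 50: +10/40 = +25.0%, +10 mm, PD |
| 4. Visceral lesion 30 to 22, plus node 32x22 to 27x12 | 62 to 49: -13/62 = -21.0%, SD | 52 to 34: -18/52 = -34.6%, PR |
| 5. Nodes 28x18 and 26x16 to 15x8 and 14x8 | 54 to 29: -25/54 = -46.3%, PR on the sum | both short axes 8 mm, below 10: target-lesion CR |

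Cases 1 to 4 show category changes in both directions, including in a patient with mixed disease. Cases 2 and 3 are opposite errors: progression called on L but not on A, and progression missed on L. The error is therefore not reliably conservative.

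Case 5 needs care. The nodal CR condition is a short-axis rule, so the 29 mm left in the longest-diameter sum does not by itself change the category. The case matters only if the short axis was never recorded, because CR could then not be established.

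**Which outcomes can move**
- Response rate (CR or PR, SAP 6.3): moved by SD/PR switches. A CR/PR switch changes only the split between the two.
- DCR (CR, PR or SD, with the 12-week minimum, SAP 5.1): moved by SD/PD switches. Switches among CR, PR and SD leave it unchanged once the 12-week minimum is met.
- PFS: moved by SD/PD switches when the target sum is what decides progression. Death, new lesions and non-target progression also count as events and do not depend on the axis.
- Tumour-size summaries (SAP Table 4, Figures 3 and 4): moved whenever a nodal target is present.
- OS: unaffected.

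For scale, SAP 3.5 sets the DCR threshold at 10 patients when 31 are enrolled. A single SD/PD switch would change that result only if the count stood at 9 or 10.

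**The case against.** The strongest reply is that the response rule is already fixed. Section 5.9.15 itself names RECIST v1.1 and Appendix A, SAP 5.1 does the same, and nothing says that response is derived from a longest-diameter sum. The quoted sentence concerns tumour size, which 5.9.15 lists separately from PFS and response rate. SAP Table 4 and the response criteria in Appendices A and B speak only of diameters, which is compatible with Appendix A. Section 5.9.15 also still refers to breast cancer metastases in a CUP trial, so the wording looks like uncorrected template text and not a second measurement rule. A site applying Appendix A has to measure the short axis anyway, to accept a node as a target and to call CR.

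Much of this stands. It makes correct classification plausible at sites that work from Appendix A, and it makes a deliberate departure unlikely. It does not remove the contradiction: 5.9.15 names the quantity to be recorded, says it twice, and gives no order of precedence.

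Stronger readings are tempting, and the documents do not support them:
- A reader might infer that nodal short axes were not collected. The lesion form and the eCRF Completion Manual (Protocol 10.4) are not among the documents, so this is unproven.
- A reader might infer that response rate, DCR and PFS are all generally unreliable. Only patients with nodal targets are exposed, and only through the switches listed in the working.
- A reader might take three nodal rows among seven CUP subtypes in SAP Table 1 as a measure of how common nodal disease is. They are row labels in an empty table, not frequencies.

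**Conclusion.** The inconsistency is real and the text of 5.9.15 is wrong against the standard it names. Where measurements were recorded as 5.9.15 says, patients with nodal target lesions can receive the wrong response or progression category, in either direction.

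The size at patient level is illustrated by assumed dimensions: a 30 x 20 mm node can differ by a full category with changes of a few millimetres. The size at trial level cannot be computed, because the documents give neither the share of patients with nodal targets nor the content of the lesion form. If the form already captures nodal status and short axis, only the wording and the table notes need correcting. The point therefore supports a prompt correction and a check of the form. It does not support a conclusion that recorded categories are wrong, or an unconditional re-derivation.

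**What to change.** 1. In Protocol 5.9.15, replace both phrases with Appendix A's rule: longest diameter for non-nodal targets, short axis for nodal targets, and the sum of these.
2. State the same rule in a footnote to SAP Table 4 and to the waterfall plot (Figure 4).
3. Check that the eCRF lesion form records whether each target is nodal and, if so, its short axis.
4. Only if it does not: add the field, enter nodal short axes from existing scans, and re-derive the affected categories before database lock.

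The cost is a wording change, two footnotes and a small amount of data checking. Step 4, if needed, adds a form change and re-entry for patients with nodal targets. No new scans are required, and sample size, power and alpha do not change.
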